9.3.4 Follow-up Variables

The following additional variables will be collected every 30 days during a 12-month period of follow-up for analysis of the primary and secondary objectives:

Dynamic eligibility variables

- Possession of an active driver's licence over the past 30 days,
- Access to a motor vehicle over the past 30 days,
- Have driven at least once in the previous 30 days, and
- Resides in the US over the past 30 days.

Medication use, migraine experience, and the use of anti-migraine medication in the past 30 days

- Migraine experience over the past 30 days: number of migraine attacks, impact of migraine on daily life),
- Use of acute and preventive anti-migraine medications over the past 30 days (medications names, dose for lasmiditan),
- Use of concomitant medications potentially associated with MVA risk (including antihistamines, antidepressants, benzodiazepines, beta-blockers, opioids, anti-seizure medications, antipsychotics, sleeping pills including sedatives and hypnotics) within the last 30 days, and
- New comorbidities declared in the last 30 days (including hypertension, hypotension, musculoskeletal diseases, ophthalmological diseases, insomnia, anxiety, diabetes, depression, other psychiatric disease, chronic insomnia, chronic fatigue syndrome, seizure disorders).

Driving characteristics and experience of MVAs for which the participant was the driver

- Change of ZIP code of residency,
- Approximate number of miles driven in the past 30 days, and
- Number and dates of self-reported MVAs for which the participant was the driver occurring during the past 30 days, details and circumstances of these MVAs (details provided below).

Details on self-reported MVAs for which the participant was the driver in the last 30 days

- Location of MVA,
- Severity of the accident (approximated by the extent of motor vehicle and property damages),
- Speed of the motor vehicle driven by the participant,
- Other vehicle(s) and/or persons involved (i.e., pedestrian, cyclist, motorcyclist, car, other vehicle),

Non-Interventional Protocol

- Perceived fault and reasoning for the accident,
- Seriousness of related injuries for any persons involved in the MVA:
 - Slightly injured: minor character of injury not requiring medical treatment such as a sprain (including neck whiplash injury), bruise or cut which are not judged to be severe, or slight shock requiring roadside attention, and
 - Seriously injured: fractures, concussion, internal injuries, crushings, burns (excluding friction burns), severe cuts, severe general shock requiring medical treatment or death), hospitalisation for the driver.

Circumstances of self-reported MVAs for which the participant was the driver in the last 30 days

- Migraine status at the time and within 24 hours of MVA,
- Use of prescribed anti-migraine medication up to 24 hours prior to the accident (preventive and acute) (medications names, dose and time since medication administration relative to the occurrence of MVA for lasmiditan),
- Symptoms immediately preceding (right before) the accident, including but not limited to aura, headache, fatigue, nausea, dizziness, somnolence, palpitations, vertigo, visual impairment, chest discomfort, muscle weakness, paresthesia, incoordination, lethargy, restlessness and anxiety,
- Use of concomitant medications potentially associated with MVA risk within 24 hours of the accident (including antihistamines, antidepressants, benzodiazepines, beta-blockers, opioids, anti-seizure medications, antipsychotics, sleeping pills including sedatives and hypnotics),
- Influence of alcohol or drugs at the time of the MVA, and
- Time of day, weather, visibility and lighting conditions at time of the accident.

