9.1.2 Phase 2: Prospective Surveys

Participants enrolled into Phase 2 of the study will create an HRS profile and complete a baseline survey assessing events in the past year and follow-up surveys are planned to subsequently be administered once every 30 days for 12 months.

Data collected in the baseline surveys will include demographics, migraine experience (including age at diagnosis, presence of aura, impact on daily life and average number of migraine attacks by month), use of prescribed anti-migraine medication, medical history (including use of concomitant medication potentially associated with MVA risk and comorbidities), driving characteristics and self-reported MVAs history (for which the participant was the driver) in the past year, as presented in Section 9.3.3. A validation of migraine diagnosis will be completed by the referring HCP after the baseline survey is completed by the participant.

Data collected every 30 days in follow-up surveys, will include any change in self-reported use of prescribed anti-migraine medication (acute and preventive) and concomitant medication potentially associated with MVA risk, recent migraine experience, self-reported MVAs (for which the participant was the driver) in the last 30-day period, circumstances of these MVAs (including not exclusively migraine status, use of prescribed anti-migraine medication 24 hours prior the accident, symptoms immediately preceding the MVA, details on environmental factors including weather), severity and impact of the accident (including property damages, injuries and hospitalisation), as presented in Section 9.3.4. Each time the monthly follow-up survey is administered to a given participant, the participant will be allotted a 7-day window to complete it.

Approximately 60% of participants will be randomly selected in each treatment group (up to 600 in each treatment group) to describe the agreement between self-reported data on prescription migraine medication use (acute and preventive) and prescription claims data.

Self-reported survey data on prescription migraine medication use (acute and preventive) will be compared with pharmacy data (including prescribed drug and dosage), obtained via linkage with ExamOne ScriptCheck (additional information in Section 9.4.3). For each randomly selected participant, the data agreement will be assessed at 2 time points: once at baseline, and once at the end of the online survey data collection period described above.

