9.4.2 Direct-to-Participant Online Surveys

The primary data source for the study will be participant profiles and direct-to-participant (DtP) online survey responses to baseline and follow-up surveys on participant's health history (particularly migraine), MVA occurrences and circumstances of MVAs (including medication use prior to MVA, migraine status and preceding symptoms), and driving characteristics, collected electronically from recruited participants using IQVIA HRS' dynamic web-based platform. Participant profile will include identifying information (name, date of birth, phone number and residential address), sex, gender, race, ethnicity, and a designated alternative contact in the event the participant cannot be contacted.

The online survey will include built-in logics module and custom logic segments to: 1) reduce the time spent by participants filling in information; and 2) minimise clean-up activities needed by coding and quality checks. The online survey system provides access to standardised operational reports on study progress and study data extracts for data management and analysis teams.

The online survey will consist of multiple-choice questions (i.e., a list of possible responses among which participants will be instructed to select the one(s) that best described what they had

experienced in the past 30 days) and is estimated to take up to 20 minutes to complete. Surveys will be completed at baseline and every 30 days of follow-up for a total of up to 12 surveys.

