9.6.4 Study Compliance and Lost to Follow-up Participants

Virtual site staff will monitor whether participants are completing the online surveys. Participants who do not complete the study steps (e.g., the baseline online survey, the follow-up online surveys) will be contacted by phone call and/or text message with reminders to complete tasks within a time window that is appropriate to the specific task; participants will remain in the study sample regardless of whether they submit data in a timely manner.

Participants who begin the enrolment registration process will remain active and able to complete their enrolment until recruitment targets are reached, at which point they will be notified the study is no longer actively recruiting.

For follow-up online surveys sent every 30 days after the baseline survey, participants will be sent an automated reminder to complete their online survey, which be available for completion for 1 week. Additional automated reminders will be sent as needed, and study staff will contact the participant via phone 1-2 days before the survey window expires to address any barriers to completing the survey. After 1 week passes, access to that follow-up online survey will close. An invitation for the subsequent follow-up survey will be sent according to the schedule determined at baseline.

If a participant does not respond to two consecutive online survey invitations, IQVIA will make no more than five additional attempts, including outbound calls and other means of communication as appropriate, to contact the participant and encouraging to respond to the most recent survey invitation, and/or the alternative contact provided at enrolment. If there is no response to the fifth attempt, the participants will be considered lost to follow-up. All available information in the participants' file through the date of last contact or survey completion will be recorded for the lost to follow-up participants. The statistical analysis plan (SAP) will specify how such participants will be considered for purposes of endpoint assessment.

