9.7.2.2.2 Primary Statistical Analysis

9.7.2.2.2.1 Data Structure and Notation

The data structure generated from the procedure illustrated in Section 9.1 will take on the general form shown in Table 5. As illustrated, each row of the data will represent an observation of a given participant at the kth interval of follow-up for the mth 'trial.' The treatment indicator A_k will take on one of three values corresponding to the treatment strategies of interest (see Section 9.1) and will be constant for a given participant within a given mth trial. Treatment history, denoted A_{k-1} , is the treatment the participant received in the prior (k-1) interval. A vector of baseline covariates, denoted L_0 , will take on fixed values across all 'k' intervals of a given participant's 'participation' in an mth trial. A vector of time-varying covariates, denoted L_k , will take on their recorded values at time 'k' in a given participant-trial. The event indicator, denoted D_{k+1} , will take on a value of one if the event occurred in the subsequent (k+1) interval, or a value of 0 otherwise (e.g., censoring).

In the data structure, the number of rows for each participant in a given mth trial will correspond to the length of follow-up. For example, in Table 5, Participant 3 participated in nested trial 7 and nested trial 9. This participant was followed-up for four intervals in trial 9 and experienced the outcome event in the 4th interval of follow-up. Notably, treatment information recorded in the 4th interval of follow-up is discarded because it is unknown whether treatment was administered before or after the outcome event within that interval. This is because the surveys only collect information and treatment data at the 30-day level.

Participant ID	Trial No. (m)	Follow -up (k)	Treatment (A _k)	Treat Hx (A _{k-1})	Baseline Covariate (L ₀)	Time- Varying Covariate (L _k)	Outcome (D _{m+k+1})	Censor (C _{m+k+1})
1	45	0	0	0	0	0	0	0
1	45	1	0	0	0	1	0	0
1	45	2	0	0	0	0	0	1
2	34	0	2	2	1	0	0	0
2	34	1	2	2	1	1	1	0
3	8	0	1	1	0	1	0	0
3	8	1	1	1	0	0	0	1
3	9	0	0	1	1	0	0	0
3	9	1	0	0	1	0	0	0
3	9	2	0	0	1	1	1	0

 Table 5.
 Generalised Longitudinal Data Structure for the Final Analysis

9.7.2.2.2.2 Statistical Models

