- 2. It may not be possible to achieve balance between all potential confounders across treatment groups (i.e., ASMD<0.1). Imbalances in baseline characteristics will be addressed with a re-specification of inverse probability weights (e.g., Changing the functional form of the variable or including interaction terms). However, if imbalances remain these will be described along with their potential impact on the outcome estimate(s).
- 3. It may not be possible to model all collected covariates due to sparsity, collinearity, or other factors that can preclude convergence of statistical models. For this reason, the final variables and functional forms of the baseline (L_0) and time-varying (\overline{L}_k) covariate vectors described in the models above will be determined at the time of analysis.
- 4. The time interval of the analysis, denoted 'k', directly influences the dimensionality of the dataset, and concequent computational intensity of the analysis. Particularly, choosing a time interval of one day will greatly increase the number of rows in the analytic data set and, concequently, increase the computation time of nonparametric bootstrap algorithms for standard error estimation. Therefore, if computation times are too great then the time interval of the analysis may be expanded accordingly (e.g., to one week or one month).

9.7.2.2.2.3 Missing Data

Missing data may arise from participants who skip a single survey only, or who are lost to followup (defined as non-responce on two concecutive follow-up surveys). Participants who are lost to follow-up will be censored at 67 days following the opening of their last survey (as participants are allotted 7 days to answer each 30-day survey). Missing data arising from non-response will be addressed using *last observation carried forward*, where the most recent survey responses are "carried forward" under the assumption that participants' treatment and confounder histories did not change during the time spanning from the participant's final response through the period of non-response.

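### Follow-up surveys ask about accidents in the past 30 days only, so a single skipped survey leaves about 30 days that are never asked about but by default count as event-free

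*Protocol*

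**What the plan says.** **Recall period.** Protocol 9.3.4 lists, for every follow-up survey, "Number and dates of self-reported MVAs for which the participant was the driver occurring during the past 30 days". The abstract, 9.1.2 and Table 4 use the same period. Section 9.4.2 describes the online questions as covering what participants "experienced in the past 30 days) and is estimated to take up to 20 minutes to complete". No item refers to the time since the previous completed survey.

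**Timing.** Surveys go out every 30 days, and for each one "the participant will be allotted a 7-day window to complete it" (9.1.2). Section 9.6.4 adds: "After 1 week passes, access to that follow-up online survey will close". Participants are not contacted afterwards to clarify or revise answers (9.8, 9.9.2).

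**Skipped surveys.** Section 9.7.2.2.2.3 foresees this: "Missing data may arise from participants who skip a single survey only". Loss to follow-up needs two consecutive non-responses, with censoring 67 days after the last survey opened (Table 1, 9.2.4.4), so one skip does not end follow-up. Responses are carried forward on the assumption that "treatment and confounder histories did not change during the time spanning from" the last response through the gap. The event indicator is 1 if an event occurred in the next interval, "or a value of 0 otherwise (e.g., censoring") (9.7.2.2.2.1).

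**Other sources.** The alternative contact may be approached only after two consecutive non-responses, and is asked only about vital status, cause of death, and hospitalisation or serious injury from an accident (9.3.5). The primary analysis population requires a completed first follow-up survey (9.7.2.2.1).

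**The concern.** The survey is the only routine source of the primary outcome, and its recall period equals the survey interval with nothing to spare. If one survey is missed, the next reaches back 30 days and no further. An accident in the missed block has no place to be reported, yet the participant remains in the risk set.

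The crude incidence rates suffer first. They become the primary result if the Lasmiditan Group is too small, which 9.5 treats as a real possibility, and they feed the comparison with national rates (9.7.3). Lost events also cost power. The loss arises when data are collected: an analysis plan can drop unasked time, but it cannot recover accidents that nobody asked about.

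**Working it through.** **1. The plan's own figure.** Inputs from 9.5 and Table 3: hazard ratio 2.0, comparator risk 3.0%, 80% power, 5% level (taken as two-sided). Freedman's formula gives

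D = (1.960 + 0.842)² × ((2+1)/(2−1))² = 70.64 events.

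The Lasmiditan risk is 1 − 0.97² = 0.0591, so n = 70.64 / (0.030 + 0.0591) = 792.8, that is 793 per group. With 20% dropout, 793 / 0.80 gives 992. Both stated figures are reproduced.

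**2. One isolated skip.** It leaves 30 / 360 = 8.3% of follow-up unasked. Skipping every second survey would never trigger loss to follow-up.

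**3. Late completion, only if the 30 days run back from completion.** A survey answered d days into its window, after one answered d₀ days into its window, leaves max(0, d − d₀) days unasked, at most 7. These are the days just after the previous survey. A first survey answered on day 37 does not cover days 1 to 7. With delays uniform over 7 days, the expected gap is 3.5 days for the first survey and 7/6 days for each of the other 11: 3.5 + 11 × 7/6 = 16.3 days, or 4.5% of 360. If the 30 days run back from survey opening, this part is zero.

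**4. Both parts together.** These figures come from simulation over 12 surveys. The first survey is always completed, and two consecutive misses end follow-up under the 67-day rule. Assumptions not in the documents: independent skips at the rates shown, and uniform completion over the window. Events = 793 × 0.0891 × (1 − f), where f is the unasked share. Power = Φ(√events / 3 − 1.960).

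| Skip rate | 30 days counted from | Unasked share f | A 3.0% risk is recorded as | Events | Power |
|---|---|---|---|---|---|
| 0% | completion | 4.5% | 2.86% | 67.5 | 78.2% |
| 0% | opening | 0% | 3.00% | 70.7 | 80.0% |
| 5% | completion | 8.8% | 2.74% | 64.4 | 76.3% |
| 5% | opening | 4.7% | 2.86% | 67.3 | 78.1% |
| 10% | completion | 13.1% | 2.61% | 61.4 | 74.3% |
| 10% | opening | 9.3% | 2.72% | 64.1 | 76.1% |
| 20% | completion | 21.7% | 2.35% | 55.3 | 69.8% |
| 20% | opening | 18.6% | 2.44% | 57.5 | 71.5% |

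A hand check for opening at 10%: 11 surveys × 0.10 × 30 days = 33 days, and 33 / 360 = 9.2%, in line with the table.

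**5. Hazard ratio.** The observed ratio is about the true ratio × (1 − f_L) / (1 − f_C), where L is the Lasmiditan Group and C the comparator. Equal shares cancel. If 15% were unasked with lasmiditan and 5% in the comparator, 2.0 × 0.85 / 0.95 = 1.79. That imbalance is an illustration only.

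**The case against.** - **The protocol never says that skipped time is event-free.** This is right. The carry-forward assumption names treatment and confounders, not the outcome. There is a separate censoring indicator, and 9.7 says missing responses will not be imputed, which sits awkwardly with carrying them forward. An analysis plan could treat the block as unobserved. What stands is that no stated rule does so, that the default for the event indicator is zero, and that dropping the time would mend the rates but not bring back the events.
- **A reader might infer that every late completion opens a gap.** The documents do not support this. They do not say whether the 30 days end at opening or at completion, and the questionnaire is not shown. Nor would the missed days be those just before completion, which are the ones covered.
- **A reader might infer that the hazard ratio is biased, or that accidents themselves cause the skips.** Neither is documented. Section 9.9.5 accepts that very serious accidents may go unreported, but it relies on the alternative contact, who does not come into play after one skip or for minor accidents.
- **Short recall is deliberate (9.9.2), and skips are discouraged by reminders and a telephone call before each window closes (9.6.4).** Both are fair. They limit the size of the loss but do not close the gap when a skip occurs.

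**Conclusion.** The concern holds for skipped surveys: each isolated skip among surveys 2 to 12 leaves about 30 days (8.3% of 360) in which no accident can be reported, while the participant remains at risk under the rules as written. The late-completion gap is conditional on how the 30 days are anchored.

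With assumed skip rates from 0% to 20%, the unasked share runs from 4.5% to 21.7% if anchored at completion and from 0% to 18.6% if anchored at opening. Incidence rates are biased low in proportion and power falls. The hazard ratio is about unchanged unless non-response differs between groups. The skip rates and completion pattern are assumptions, and the finding rests on the protocol's variable definitions rather than the survey itself.

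**What to change.** In 9.3.4, 9.1.2 and Table 4, change only the accident item (number, dates and circumstances) so that it covers the time since the last completed survey, with that date displayed by the platform. For the first follow-up survey, use the time since the baseline survey. Place each event in its interval by its reported date, which is already collected.

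Leave the medication and eligibility items at 30 days. A reader might think they should be widened too, but exposure is defined by use in the prior 30 days (9.1) and routine medication use carries no dates. One answer spanning two intervals could not be split, and any-use exposure would become likelier after a skip. Leave the lost-to-follow-up rule unchanged.

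The cost is one displayed date and a reworded item. The downside is accident recall of about 60 to 67 days after one skipped survey. That is longer than planned but well short of the 12 months asked about at baseline, which the protocol itself interprets cautiously.

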9.3.5 Additional Contact

In the event that participants do not respond to two consecutive survey invitations, the alternative contact provided as part of profile creation may be contacted. The following information will be solicited from the alternative contact:

- Vital status of the study participant,
- (If deceased) Cause of death for the study participant, including whether it was related to an MVA, and
- Hospitalisation or serious injury related to MVA for the driver.

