9.1 Study Design

This is an observational cohort study, aiming to compare the one-year risk of MVA associated with three treatment strategies of interest, in patients with migraine in the US. The comparative treatment strategies of interest, as well as other core elements of the study design, are described in Table 1. No visits, examinations, laboratory tests, or procedures are mandated or recommended as part of this study.

Eligibility Criteria	 Participant age is 18 to 74 years old at enrolment; Participant has a valid driver's licence that they received ≥1 year before enrolment; Participant has access to a vehicle at the time of enrolment and anticipates having access to a vehicle for the next 12 months (at enrolment); Participant must confirm having driven at least once during the 6 months prior to enrolment; Participant must provide informed consent to participate in this study; Participant must be able to read and understand English; Participant must currently reside in the US; Participant must have access to a personal device with internet connection; Willing to complete study surveys once every 30 days for 12 months at enrolment; and Participant must be willing to provide consent to access their antimigraine medication prescription claims data from ExamOne ScriptCheck and allow HCP to confirm migraine diagnosis, completing the Health Insurance Portability and Accountability Act of 1996 (HIPAA) Authorisation/Medical release Form.
Treatment strategies	 Use of lasmiditan exclusively or in conjunction with other acute antimigraine migraine medication for up to one year; Use of any non-lasmiditan prescribed acute anti-migraine medication (see medications list in Annex 3) for up to one year; and No use of any prescribed acute anti-migraine medication for up to one year. Self-reported use of prescribed acute anti-migraine medications will be utilised to assign treatment exposure category. The self-reported use of prescribed preventive anti-migraine medication will not be considered for treatment group classification

Table 1.Core Study Elements for The Primary Analysis using a 'Nested Trial'
Approach

Outcome	Self-reported first occurrence of MVA for which the participant was the driver since study enrolment.

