9.9.5 Missing Data and/or Dropout

Missing items will not be permitted by the online survey and so intermittent missingness is not expected. Anticipated missing data could be due to participants exiting the questionnaire before completion and as for any longitudinal study, attrition and loss-to-follow-up may occur. However, participants may not complete all surveys included as part of the study design (e.g., every 30 days for 12 months).

It could also happen that a participant has a very serious/severe accident and due to injuries or death, information will not be known/reported for the study, which could lead to underestimation of MVA incidence. This will be mitigated by requiring participants to designate an alternative contact who can confirm information if the participant is unable to be reached (see Section 9.3.5 for details of what may be requested from the alternative contact) Missing data arising from non-response will be addressed using *last observation carried forward*, (See Section 9.7.2.2.2.3).

10. Protection of Human Subjects

This study will be submitted to at least one ethical review board (ERB) for review and to confirm that the study is considered non-interventional. Regulatory authorities will be notified and approval sought as required by local laws and regulations. This observational study will be performed in accordance with ethical principles that are consistent with the Declaration of Helsinki (WMA 2013), the ICH guideline E6R1 (International Council for Harmonisation 1996) and the Good Pharmacoepidemiology Practices (GPP) issued by the International Society for Pharmacoepidemiology (ISP 2015) and the applicable legislation on non-interventional studies and/or observational studies.

11. Management and Reporting of Adverse Events/Adverse Reactions

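### Section 9.3.5 does not ask the alternative contact whether a participant killed in an MVA was driving, or when any crash happened

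*Protocol*

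**What the plan says.** Table 1 in Protocol Section 9.1 defines the outcome as "Self-reported first occurrence of MVA for which the participant was the driver since study enrolment". Section 9.7.2.2.2.1 codes an event by the follow-up interval in which it occurs. The participant's own survey is built for this: Section 9.3.4 collects "Number and dates of self-reported MVAs for which the participant was the driver occurring during the past 30 days".

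Section 9.9.5 accepts that after a severe crash, "due to injuries or death, information will not be known/reported for the study, which could lead to underestimation of MVA incidence". Its answer is "requiring participants to designate an alternative contact who can confirm information if the participant is unable to be reached", and it refers to Section 9.3.5 for the content of the enquiry.

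Section 9.3.5 applies after two consecutive unanswered invitations. It opens with "The following information will be solicited from the alternative contact" and lists three items:

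- "Vital status of the study participant"
- "If deceased) Cause of death for the study participant, including whether it was related to an MVA"
- "Hospitalisation or serious injury related to MVA for the driver"

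**The concern.** An endpoint event needs two facts: that the participant was driving, and when the crash happened. The injury item carries the driver condition. The death item, directly above it, does not, so a passenger's or pedestrian's death would satisfy it just as well. Neither item asks for a date.

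For these crashes the contact may be the only source. A participant who has died cannot be asked later. A survivor who resumes is asked only about the past 30 days (Section 9.3.4), and each missed survey closes after one week (Section 9.6.4). At stake is whether the safeguard against under-counting the most severe crashes yields usable endpoint data.

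**Working it through.** **1. Facts needed against facts collected**

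| Fact | Participant survey (9.3.4) | Contact: death item | Contact: injury item |
|---|---|---|---|
| Participant was the driver | Yes | Not asked | Yes |
| Date of crash | Yes | Not asked | Not asked |

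The driver gap is confined to deaths. The date gap covers both items, and the vital-status item does not list a date of death either.

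**2. How far timing is bounded without a date**

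Take day 0 as the opening of the last survey the participant answered.

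- Censoring: 30 + 30 + 7 = 67, which reproduces the plan's day 67.
- The first missed survey opens on day 30 and closes on day 30 + 7 = 37. The second opens on day 60 and closes on day 67.
- The contact enquiry requires both to be missed, so it comes at about day 67 or later. Section 9.6.4 allows up to five further attempts.
- The last completed survey was submitted between day 0 and day 7. With nothing else known, the window is at least 67 − 7 = 60 days, or two 30-day intervals.

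Two cases follow:

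- *The crash caused the silence.* To explain both missed surveys it must precede about day 37, and so it falls before day-67 censoring. The interval may still be unsettled: the window can straddle day 30, and it spans several intervals if k is a day or a week. Section 9.7.2.2.2.2 allows k to be widened to a month.
- *Non-response began for another reason.* The only upper bound is the contact date, which may lie beyond day 67. Whether the crash preceded censoring is then unknown.

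Treatment assignment is not affected in either case, because Section 9.7.2.2.2.3 carries treatment and confounders forward unchanged through non-response.

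**3. Scale**

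The plan targets 3 × 1000 = 3000 participants at 3% per year (Section 9.5). That gives 3000 × 0.03 = 90 MVAs with full enrolment, no excess risk and complete follow-up. The documents give no share of severe crashes. If 1% to 5% are fatal or incapacitating (an assumption), this is 0.9 to 4.5 events, of which deaths are only a part.

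As an extreme case, suppose k events are lost and all come from the lasmiditan group, with 793 per group. The risks are 3.0% and 1 − 0.97² = 5.91% (Table 3 shows 5.9%). Expected events are 793 × 0.03 = 23.8 and 793 × 0.0591 = 46.9. The approximate HR is (46.87 − k)/23.79, and the SE of its log is √[1/(46.87 − k) + 1/23.79].

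| Events lost (k, assumed) | Approximate HR | 95% CI |
|---|---|---|
| 0 | 1.97 | 1.20–3.23 |
| 2 | 1.89 | 1.15–3.10 |
| 5 | 1.76 | 1.06–2.91 |

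This is a crude ratio that ignores weighting and covariates. It serves for scale only.

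**The case against.** The case on the other side has several parts.

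- *Section 9.3.5 lists topics and is not a script.* It does not say that nothing else may be asked, and Section 9.9.5 describes the same list more permissively. Asking who was driving would fit naturally under cause of death. This is fair, but nothing requires the question to be asked or the answer recorded.
- *The missing driver condition may be shorthand.* The protocol often writes MVA alone when it means the driver endpoint, and Section 9.3.4 includes death in its serious-injury category. But Section 9.3.5 gives death its own item and puts the driver condition only on the next one.
- *Section 11 offers another route.* Driver MVAs and associated fatal outcomes are protocol-defined adverse events. However, no passage says that driver status or a crash date is obtained from the contact for this purpose.
- *Section 9.6.4 leaves endpoint handling of lost participants to the SAP.* It does, but an SAP cannot recover facts that were never collected.
- *Timing is bounded, and the numbers are small.* Both stand, and they limit the point as stated in the verdict.

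**Conclusion.** The point holds in a limited form. As the list stands, a contact-reported MVA death cannot be classified against the driver endpoint. Contact-reported crashes, fatal or not, can be timed only between the last completed survey and the contact date. That may not settle the interval or, where non-response had another cause, whether the crash came before censoring. The mitigation in Section 9.9.5 is weakened but not void.

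A reader might infer more than the documents support:

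- *That no contact-reported crash can be used.* Non-fatal reports carry driver status, and a crash that explains both missed surveys falls before about day 37.
- *That crashes might be credited to the wrong treatment.* Treatment is carried forward through the gap.
- *That non-driver deaths would be counted as driver crashes.* No passage says that MVA deaths enter as events by default.

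The effect on the hazard ratio is probably small. The 1% to 5% share and the values of k are assumptions, and 90 events presumes full enrolment although Section 9.5 anticipates difficulty recruiting the Lasmiditan Group. The case for a change rests on the severity of these events and the low cost of asking.

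**What to change.** In Section 9.3.5:

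1. Add to the death item whether the participant was the driver in the MVA.
2. For both the death and the injury items, add the date of the MVA, and for deaths also the date of death. Accept the month if the day is unknown.

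State that these answers will be used to classify the event as a driver MVA or not, and to assign its follow-up interval.

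The cost is two extra questions in an existing enquiry and an ethics-board notification, with no additional contacts or staff. Some contacts will not know the exact date, so part of the timing uncertainty will remain.
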